8.8 Ng and Ct therapy in the study

The study will follow current best practice guidelines for the treatment of ***asymptomatic*** Ng and Ct infections:

Chlamydia

Doxycycline is recommended as first line therapy for chlamydia urethritis and proctitis [42, 43]. As such the study will recommend (in the absence of other clinical or other reasons) to treat these infections with 7 days of doxycycline 200mg per day per os. Wherever possible all positive chlamydia samples will be sent for assessment as to whether or not they are L-serovars.

Gonorrhoea

Wherever possible the current recommended therapy of ceftriaxone 500mg or 1g IMI x one dose plus azithromycin 2g PO x one dose will be used for Ng infections [44, 45].

For ***symptomatic*** Ng infections the same protocol will be used. For ***symptomatic*** chlamydia proctitis (such as a positive Ct NAAT), 7 days doxycycline may not be long enough to treat symptomatic LGV disease. As a result, the study doctors will either confirm that the Ct is not an LGV serovar (via NAAT) within 7 days and then treat with 7 days doxycycline or else treat with doxycycline 200mg per day for 21 days [46].

8.9 Table of trial procedures

Table 2. Trial procedures

Procedures	Screening / Enrolment (V1)	Visit Month 3	Visit Month 6	Visit Month 9	Visit Month 12	Unscheduled visits (USV)
Eligibility	x					
Informed Consent	x					
Randomization	x					
Physical examination (if indicated)	x	x	x	x	x	x
STI history	x	x	x	x	x	x
Antibiotic usage	x	x	x	x	x	x
Pharyngeal swab	x ¹	x	x	x	x	x
Molecular Ng/Ct Testing						
Anorectal swab	x ¹	x	x	x	x	x
Molecular Ng/Ct Testing						
Urine	x ¹	x	x	x	x	x
Molecular Ng/Ct Testing						
Results of syphilis and HIV testing (performed according to routine practice)	x	x	x	x	x	x
Question regarding sexual behavior: How many sexual partners since last visit)	x	x	x	x	x	
PrEP questionnaire at ITM	x	x	x	x	x	
FGD on experience and preference of screening at ITM					x	

1. Sample collected according to standard practice of the participating sites.

8.10 Laboratory procedures

Ng/Ct testing:

Laboratory testing for Ng/Ct from HSP and EH will be performed at the LHUB and for all specimens from the ITM, CHU, UZG at their STI laboratories.

- CT/NG molecular testing will be performed on urine, anorectal and pharyngeal samples.
- Each laboratory will pool each individual's pharyngeal, rectal and urine specimens at each visit and thereby conduct one NAAT (Nucleic Acid Amplification Test), instead of three, according to a validated pooling strategy. Two laboratories participating in this study have published studies validating this pooling strategy [47, 48]. Another pooling strategy validated by ITM will be published soon. Pooling will considerably reduce laboratory costs.
- In case a sample is found to be positive for Ct, the samples will be sent to the Reference STI Laboratory (ITM) where an additional test will be performed to differentiate L versus non-L strains according to current routine care at each centre.

- All study samples found to be positive for Ng or Ct will be stored at each centre until the end of the study and will then be sent to the ITM for long-term storage (future STI research).

HIV and syphilis testing:

- Syphilis, HIV testing will be performed according to each laboratory algorithm as in routine practice

PrEP users who declined participation in the Gonoscreen study will be asked whether they can be invited to participate in this qualitative research part. Potential FGD participants will be explained that their point of view is of interest to the researchers and in no way wrong. They are free to decline at any time. The persons responsible for the informed consent procedure of the Gonoscreen study will keep a list with the contact details of those agreeing to be invited for this qualitative research part. This includes participants refusing participation in the Gonoscreen study. This list will be stored on a secured ITM server and password-protected. Participants who do agree to participate in the Gonoscreen study will be able to already indicate on the informed consent whether they can be invited to participate in the qualitative research part. Participants will be randomly recruited from both lists (e.g. every tenth PrEP user).

The FGDs will be conducted in a private environment (eg. a meeting room at the study site). The topic guide will include questions to enhance discussion on sexual health, STI prevention and the role of screening for STIs. Given the sensitivity of the topic we will use group exercises and cases, in which people can refer to third-persons rather than personal experiences. The topic guide will be pilot tested during one FGD with at least 6 PrEP users or research team members. The moderators will be researchers with considerable experience in qualitative research and knowledge of the subject. They will carefully facilitate the group dynamics in a way that participants can freely express themselves and their potentially different opinions on screening strategies.

To mitigate the difficulties of conducting the FGDs in the COVID-19 period, we foresee the possibility to conduct these FGDs via an online platform 'ZOOM', which is HIPAA (Health Insurance Portability and Accountability Act) compliant. This will be a professional ZOOM package, using restricted settings for higher security (e.g. waiting room function, meeting ID and required password for joining a session). We will arrange the settings such so that participants can see each other (if they consented) and the interviewer(s) to encourage the dynamic of the group discussion. We will also encourage participants to use a background function in order to not reveal details of their private homes to increase their privacy.

Data analysis

8.12 Withdrawal criteria

8.12.1 Discontinuation of trial procedures

The Investigator has the right to withdraw participants from the study if the following event occur:

- The participant tests HIV positive before the 12th month visit (see below)
- The Investigator judges that further participation would have negative effect on the participant's mental and/or physical health
- The participant wishes to stop the trial procedures

In the event of a study participant discontinuing the trial procedures, their data will be used in the analysis up to the timepoint they withdraw.

8.12.2 Withdrawal of consent (discontinuation of trial participation)

In accordance with the Declaration of Helsinki, ICH Good Clinical Practice Guidelines and the Belgian Law on experiments of 2004, a participant has the right to withdraw from the study at any time for any reason without prejudice to his/her future medical care by the physician at the institution. For the purposes of this trial, withdrawal is defined as: The participant would like to withdraw consent from study and is not willing to be followed up for the purposes of the trial at any further visits (i.e. only data collected prior to the withdrawal of consent can be used in the trial analysis).

The details of withdrawal should be clearly documented in the participant's medical records and in the electronic Case Report Form (eCRF).

Handling of Withdrawals

A complete final evaluation should be made at the time of the participant's withdrawal (discontinuation of all study procedures). The End of Study form in the case report form should be completed with an explanation of why the participant is withdrawing.

Participants withdrawn from study will continue to receive standard of care for their condition. This includes, if needed care of any adverse event or complication, whether related or not to the study procedures. The Principal Investigator (PI) will assure this standard of care is provided and he will discuss specific cases when needed with the Coordinating Investigator.

8.12.3 Loss to follow-up

A participant will be considered lost to follow-up at study closure if he discontinued study visits without informing the study staff and could not be traced. When the investigator has no news of the participant, he/she must make every effort to contact him, to establish the reason for the discontinuation of treatment, and to suggest the participant comes to an end-of-study visit. If all these attempts to contact the participant fail, the investigator can then declare the participant "lost to follow-up". The investigator should document all these attempts in the corresponding medical file.

8.12.4 Termination of the study

The study may be prematurely closed or interrupted by the sponsor in case of futility or adverse health outcomes for the study participants. The decision to interrupt the study will be taken by the trial steering committee after consultation with the independent safety experts (DSMB) (See Appendix 1).

If the study is prematurely terminated or suspended, the Sponsor will promptly inform the investigators/institutions and the EC's of the termination or suspension and the reason(s) for the termination or suspension.

8.13 End of trial

The end of the trial is considered the date of the last visit of the last participant. The applicable ECs/ Institutional Review Boards (IRBs) will be informed within 90 days of the end of trial.

9 TRIAL INTERVENTION

9.1 Name and description of intervention(s)

The intervention in this trial will be to **not** screen PrEP recipients for STIs (Ng and Ct) every 3 months compared to the current Belgian guidelines of screening every three months at 3 sites (3x3 screening).

9.2 Legal status of the intervention

Belgian HIV Pre Exposure Prophylaxis (PrEP) guidelines currently recommend 3x3 screening (screening 3-sites -pharynx, rectal and urethral- at 3 monthly intervals) for all PrEP recipients. The intervention is thus not in line with the current Belgian guidelines. The study was however developed within BREACH (who were responsible for the development of the Belgian Guidelines) as a means to provide empirical evidence as to whether or not the currently recommended 3x3 screening strategy is associated with a reduction in incidence of Ng plus Ct.

9.3 Intervention schedule

Participants in the intervention arm will **not** be screened for Ng/Ct for a period of 12 months, in reference to the routine practice of screening (and treating screening-positive) participants every 3 months.

More specifically, participants in the intervention arm will have 3 site (urethra, pharynx and rectum) sampling performed every 3 months but these testing results will only be reported at the end of the 12 month period.

10 SAFETY RECORDING AND REPORTING

10.1 Recording of safety findings in function of the available evidence

10.1.1 General considerations for the recording of safety findings

The largest safety concerns for this study are that the participants in the non-screening arm (and their partners) may experience an increase in the incidence of symptomatic Ng/Ct. Since

symptomatic Ng/Ct infections occur fairly frequently (over 10% symptomatic urethral Ng per year [50]) even in the presence of 3x3 screening in MSM PrEP cohorts, it is not optimal to define them as adverse events of non-screening.

Rather than reporting each symptomatic episode of Ng/Ct as an adverse event, the independent DSMB will evaluate if the non-screening arm has an unacceptably high incidence of symptomatic Ng/Ct. For this purpose, the DSMB will include two independent STI experts (Infectious Disease Physicians/Epidemiologists) and the study statistician who will together decide what threshold they determine to be an unacceptable risk and what methodology to use to evaluate this risk. As the number of STIs occurring during the study is also the main outcome of the trial, all STIs will be recorded both in the source documents and in the eCRF.

Our proposal will be to evaluate the incidence of symptomatic Ng + Ct in both arms at two time points: once 50% and 100% of all study recruits have passed their 6 month visit. If the incidence of symptomatic Ng + Ct in the non-screening arm is more than two-fold higher than the screening arm then serious consideration should be given to stopping the study.

10.2 Responsibilities

Principal Investigator (PI):

The PIs and delegated study doctors at each study site will be responsible for ensuring that all episodes of symptomatic Ng/Ct infections are adequately investigated, treated, followed up and reported so as to allow a timely assessment of any excess incidence of symptomatic Ng/Ct in the non-screening arm.

They will also be responsible for correct documentation of these STIs in the source documents and in the corresponding eCRFs.

Sponsor:

1. The sponsor will be responsible for the central data collection of these STIs through the eCRF database.
2. The sponsor will be responsible for informing the Trial Steering Committee (in particular the two independent experts) at 6 and 9 months of the amount of STIs that have occurred since the start of the study.

TSC:

The TSC (two independent STI experts in particular) will be responsible for evaluating the STI incidence at regular intervals and advising the sponsor on continuation of the trial.

10.3 Notification of deaths

Any deaths of study participants will be reported within 7 days to the sponsor. In case a participant dies during the study, this will be reported in the source documents and in the eCRF.

10.4 Reporting urgent safety measures

If any urgent safety measures are taken the CI/Sponsor shall immediately and in any event no later than 3 days from the date the measures are taken, give written notice to the relevant EC of the measures taken and the circumstances giving rise to those measures.

11 STATISTICS AND DATA ANALYSIS

Statistical analysis of the study will be performed by the biostatistician at the CTU according to a SAP approved before unblinding of the study statistician.

11.1 Sample size calculation

The primary endpoint is the number of diagnoses of Ng plus Ct over the study period (12 months) whilst individuals are screened vs. not screened.

Numerators: Cumulative number of diagnoses of Ng plus Ct in 12 months in screening/non-screening arms. Each participant can only contribute one diagnosis of Ct and one diagnosis of Ng per (scheduled or unscheduled) visit - regardless of number of sites infected. Thus each participant can contribute up to 2 diagnoses (Ct/Ng) at each (scheduled or unscheduled) visit. The numerator includes laboratory-confirmed diagnoses made between scheduled visits, performed inside or outside of the study.

Denominators: Number of scheduled study visits with available results for the diagnosis of Ng/Ct. The denominator does not include unscheduled visits.

Testing for these infections is performed at each three-monthly visit, i.e. 4 follow-up visits per subject (if complete follow up). Ng/Ct are tested for at 3 sites at each visit – rectum/pharynx and urethra. If a participant is found to be infected with one of these infections at more than one site on a particular visit this is counted as a single infection. If they are found to have both Ng and Ct at a visit this is classified as 2 infections.

Based on the Be-PrEP-ared study from ITM, we assume at baseline visit 79% have 0 diagnoses (pre treatment), 18% have 1 diagnosis (either NG or CT) and 3% has 2 diagnoses (both NG and CT). With screening, the number of diagnoses in the Follow Up (FU) visits depends on number of diagnosis at baseline and is shown below.

	0 diagnoses [#]	1 diagnosis [#]	2 diagnoses [#]	Average nr of diagnoses
0 diagnoses at baseline	86%	13%	1%	0.15
1 diagnosis at baseline	76%	20%	4%	0.28
2 diagnoses at baseline	71%	24%	5%	0.34

[#]These columns refer to the percentage of participants who have 0/1/2 diagnoses at each follow-up visit. In other words, of those with 0 diagnoses at baseline (first row), at each of the visits at 3,6,9 and 12 months, 86% will have 0 diagnoses, 13% will have 1 diagnosis and 1% will have 2 diagnoses.

Over 4 FU visits, this yields an average of 0.72 diagnoses per subject. Using a Poisson regression model with $\log(\text{number of visits})$ as offset, the 95% confidence interval of the log ratio (no screening vs. screening) is calculated. The 'no screening' arm is considered to be non-inferior if there is an increase of maximal 25% in number of diagnoses (i.e. increase of an average of 0.72 to 0.90 per 4 visits). The 'no screening' arm is proven to be non-inferior if the upper limit of the 95% confidence interval is lower than $\log(1.25)$. The required sample size to detect non-inferiority of the 'no screening' arm is calculated by simulation, assuming no difference between arms.

Assuming that 95% of the participants will have data on all 4 visits, and 5% will have data on only 3 visits, the required sample size to obtain 80% power is 912. Assuming an additional 10% drop out rate we will need to enroll 1014 participants.

The current number of PrEP participants at the ITM/HSP/EH/CHU/UZG is 803/739/290/260/240, respectively. At all 5 centres this number is increasing by approximately 20% per year. 99.7% of these individuals are MSM and over the age of 18. We estimate that 80% of the 2332 PrEP participants in these five centres will agree to participate. This number (n=1866) exceeds the number we need to enroll in the study (n=1014). By the commencement of the study (begin 2020) we estimate we will have 1518/886/464/314/298 individuals in the PrEP cohorts at the ITM/HSP/EH/CHU/UZG whom we will be able to screen for participation.

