- ***The biology of Ng and Ct host interactions make them less amenable to screening than HIV, syphilis and hepatitis C*** [16]. In the case of Ng, numerous aspects of the way it circulates in MSM decrease the probability that screening will be beneficial. Symptomatic disease is thought to typically occur soon (2–21 days) after infection. If symptoms do not develop, the infection (particularly in the pharynx and rectum) tends to persist in a low abundance state for one to 6 months [27]. Highly exposed individuals develop a type-specific immunity but this immunity is largely ineffective in low exposure individuals [27, 28]. The vast majority of Ng infections are asymptomatic and self-limiting in this population [27, 28]. Screening is far more likely to diagnose infections in the 6 month asymptomatic tail phase (when Ng abundance is likely lower and therefore less infectious) than in the acute first weeks post infection. These features reduce the probability that screening will decrease either symptomatic infections or Ng transmissions—assuming that the low abundance infections are less infectious. Similar considerations apply to Ct. In the case of *C. trachomatis* there is however better evidence that treatment of Ct results in “arrested immunity” and thereby paradoxically increases the probability of reinfection and may even lead to increases in prevalence [29, 30].
- ***High risk of inducing AMR.*** As noted above, gonorrhea/chlamydia screening in MSM can result in exposure levels to macrolides/cephalosporins that are strongly associated with resistance in Ng, *Treponema pallidum* and a range of other bacteria [8-10].

The fact that we have no clear evidence of 3x3 Ng/Ct screening being beneficial in this population combined with the fact that this policy results in such high rates of antimicrobial consumption in this population mean that randomized controlled trials are urgently required to assess the utility of 3x3 screening [16].

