4.3 Endpoints

4.3.1 Primary endpoint

Incidence of Ng plus Ct detected at any site whilst individuals are screened vs. not screened.

Numerators: Cumulative number of diagnoses of Ng plus Ct in 12 months in screening/non-screening arms. Each participant can only contribute one diagnosis of Ct and one diagnosis of Ng per (scheduled or unscheduled) visit - regardless of number of sites infected. Thus each participant can contribute up to 2 diagnoses (Ct/Ng) at each (scheduled or unscheduled) visit. The numerator includes laboratory-confirmed diagnoses made between scheduled visits, performed inside or outside of the study.

Denominators: Number of scheduled study visits with available results for the diagnosis of Ng/Ct. The denominator does not include unscheduled visits^a.

The diagnosis of Ng and Ct will be made via nucleic acid amplification testing (NAAT) performed on rectal and pharyngeal swabs and urine.

In the primary analysis, the primary endpoint (as described above) includes all Ng/Ct diagnoses. Hence it is implicitly assumed that every diagnosis is a new infection. It is however possible that an Ng/Ct infection detected at the 3 to 12 month visit in the non-screening arm is simply a non-resolved infection from the prior visit (see Figure 5)^b. This could spuriously increase the measured incidence in the non-screening group. Because

^a The rationale for this definition of the denominator is to, as closely as possible, reflect time at risk of testing Ng/Ct positive. If an individual misses one of their 4 study follow up visits then this reduces their probability of being diagnosed with Ng or Ct by one quarter (assuming no other relevant variables change). Our denominator definition takes this into account by only including study visits where we have results of Ng/Ct testing. Unscheduled visits are not included as these make up a very small proportion of all visits and could be considered to bias the time at risk estimate.

[figure not shown]
^b Given the natural rate of clearance of Ng and Ct from each site, this probability is very low

this risk only applies to the non-screening arm it results in a bias towards exaggerating the effect of screening on incidence. As such if our study finds that non-screening is non-inferior to screening this finding could not be explained by this bias. In a sensitivity analysis, the numerator of the primary endpoint will only include diagnoses if there was a negative test result at the prior visit.

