This is further illustrated for gonococcal infections in Figure 5, where over the 12 month follow up there are 4 incident Ng infections in the 4 individuals considered in the no-screening arm. These 4 incident infections are classified according to the study methodology. These 4 infections actually occurred in 2 individuals on 2 contiguous visits meaning it is possible (though very unlikely) that the second of each of these infections represent merely the end stages of the natural elimination of the first infection which still test positive on Ng Nucleic Acid Amplification Test (NAAT).

This would not occur in the screening arm where both these infections would be treated and eliminated at the visit at which they were first detected. The net effect would be a spurious high incidence of Ng in the no-screening arm. Similar considerations would apply to Ct. Because this bias exaggerates the effect of screening, if our study finds that no-screening is non-inferior to screening then this finding could not be explained by this bias.

Figure 5. The non-resolved infections bias

Test of cure: The studies approach to positive Ng/Ct test results at a test of cure visit is outlined in the 'Test of cure visit' section on page 30 (section 8.4).

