- **Day-of-visit testing.** The tests for Ng/Ct and other laboratory tests are performed on the day of the clinic visit. The participant is typically contacted the following week in the event of an abnormal laboratory test for further treatment/intervention.
- **Week-prior testing.** Here the laboratory tests are performed the week prior to the clinic visit and the results are available to discuss during the clinic visit.

The results of these tests will be used for documentation purposes after the participant has given consent to participate. The test itself is to be considered as a standard of care screening test.

In the event of a positive test for Ng/Ct at this screening visit, they will receive appropriate therapy regardless of which arm they are assigned to.

If an individual has ***symptomatic*** urethritis or proctitis at the time of the study visit they will not be eligible for study enrolment at that visit. They will however be eligible for enrolment at one of their subsequent study visits if their symptoms have resolved by this time point.

Testing positive for syphilis and receiving treatment for syphilis is not an exclusion criteria for participation at the screening or any other visit.

Eligibility for study participation will be confirmed by the study doctors. Study participants will not receive any reimbursement for participation.

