8.7 Trial assessments

These assessments will be performed according to standard of care at each participating centre. In certain centres such as HSP the laboratory tests are performed the week before the clinic visit. These laboratory assessments will be considered to be the laboratory results for that particular visit. Participants in the non-screening arm will not be informed of their results at month 3, 6 and 9. They will only be informed about the result of the sample taken at month 0 and month 12.

Screening/enrolment visit (Day 0):

- Eligibility check
- Informed Consent Procedure
- Demographic and question regarding sexual behaviour
- PrEP questionnaire (only at ITM)
- Ask if symptoms compatible with STI
- Physical examination if symptomatic
- STI history last 12 months
- Antibiotic usage last 6 months
- Randomization
- Collection of results of syphilis and HIV testing (performed according to routine practice)
- Sample collection (according to standard practice of the participating sites.):
 - o Urine sample (first-void) (Ng/Ct NAAT)
 - o Pharyngeal swab (Ng/Ct NAAT)
 - o Anorectal swab (Ng/Ct NAAT)

Visit month 3 (can be between one week earlier and 6 weeks later):

- Ask if symptoms compatible with STI
- Physical examination if symptomatic
- STIs diagnosed since last visit (at study site or outside)
- Antibiotic usage
- Question regarding sexual behaviour
- PrEP questionnaire (only at ITM)
- Collection of results of syphilis and HIV testing (performed according to routine practice)

- Sample collection:
 - o Urine sample (first-void) (Ng/Ct NAAT)
 - o Pharyngeal swab (Ng/Ct NAAT)
 - o Anorectal swab (Ng/Ct NAAT)

Visit month 6 (can be between one week early and 6 weeks late):

- Ask if symptoms compatible with STI
- Physical examination if symptomatic
- STIs diagnosed since last visit (at study site or outside)
- Antibiotic usage
- Question regarding sexual behaviour
- PrEP questionnaire (only at ITM)
- Collection of results of syphilis and HIV testing (performed according to routine practice)
- Sample collection:
 - o Urine sample (first-void) (Ng/Ct NAAT)
 - o Pharyngeal swab (Ng/Ct NAAT)
 - o Anorectal swab (Ng/Ct NAAT)

Visit month 9 (can be between one week early and 6 weeks late):

- Ask if symptoms compatible with STI
- Physical examination if symptomatic
- STIs diagnosed since last visit (at study site or outside)
- Antibiotic usage
- Question regarding sexual behaviour
- PrEP questionnaire (only at ITM)

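### The carry-over sensitivity analysis restricts the numerator but not the denominator, and 11.1 does not link its equal-arms assumption to carry-over

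*Protocol*

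**What the plan says.** **Sizing.** Protocol 11.1 says the required sample size for the no-screening "arm is calculated by simulation, assuming no difference between arms". The input rates are those seen under screening: "With screening, the number of diagnoses in the Follow Up (FU) visits depends on number of diagnosis at baseline". The result is 912 participants for 80% power, or 1014 after 10% drop-out.

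**Carry-over.** The primary endpoint treats every positive as a new infection. Protocol 4.3.1 says of unresolved infections: "This could spuriously increase the measured incidence in the non-screening group". It adds that the bias runs against non-inferiority. Footnote b judges its size: "Given the natural rate of clearance of Ng and Ct from each site, this probability is very low". The text on Figure 5 agrees: "it is possible (though very unlikely) that the second of each of these infections" are the tail of the first. Neither place gives a number. The only duration in the documents is in Protocol 1, where asymptomatic Ng "tends to persist in a low abundance state for one to 6 months".

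**Where recounting can arise.** Participants positive at the screening visit are treated in both arms: "they will receive appropriate therapy regardless of which arm they are assigned to" (Protocol 8.1.2). After that, "Participants in the non-screening arm will not be informed of their results at month 3, 6 and 9" (Protocol 8.7). Recounting is therefore possible at months 6, 9 and 12, in the unscreened arm.

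**Sensitivity analysis.** Protocol 4.3.1 and SAP 5.2 and 7 limit the numerator to diagnoses with a negative test at the preceding visit. No change to the denominator is stated. SAP 3 recodes an out-of-window scheduled visit as unscheduled and marks the scheduled one as not done.

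**The concern.** A visit that follows a positive test can never add an event under the restricted rule, yet it still counts as exposure. If such visits were equally common in both arms this would cancel. They are not equally common when infections persist without treatment, or when acquisition is truly higher without screening. The unscreened rate is then diluted more than the screened rate. This is the analysis a reader will turn to if the primary comparison fails, so it should not lean either way. It also has two loose ends: the prior visit has two readings once a visit is recoded as not done, and the rule does not say whether the negative test must be for the same pathogen.

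The second point concerns 11.1. A ratio of 1.00 in counted diagnoses differs from a ratio of 1.00 in acquisition whenever infections are recounted in one arm. A failed primary result could then reflect recounting rather than a benefit of screening, and 11.1 gives no view of how fast power falls as the measured ratio moves away from 1.00.

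**Working it through.** **1. The plan's own figure.** Inputs from Protocol 11.1: baseline classes 79/18/3%; 0.15, 0.28 and 0.34 diagnoses per visit; 95% with four visits and 5% with three; margin 1.25; two-sided 95% interval.

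- Per visit: 0.79×0.15 + 0.18×0.28 + 0.03×0.34 = 0.1791. Over four visits: 0.7164, the plan's 0.72.
- Mean visits: 0.95×4 + 0.05×3 = 3.95. Expected diagnoses per arm of 456: 456×0.1791×3.95 = 322.6.
- SE of the log ratio at 1.00: √(2/322.6) = 0.0787.
- Power: Φ(0.2231/0.0787 − 1.96) = 81%. The closed-form total for 80% is 892. Simulating the 11.1 table at 912 gives 79%. So 912 reproduces, and 912/0.9 gives 1014.

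**2. Power at 912 by measured ratio R.** Power = Φ(ln(1.25/R)/SE − 1.96), with SE = √(1/322.6 + 1/(322.6R)).

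| R | ln(1.25/R) | SE | Power |
|---|---|---|---|
| 1.00 | 0.2231 | 0.0787 | 81% |
| 1.03 | 0.1936 | 0.0782 | 70% |
| 1.05 | 0.1744 | 0.0778 | 61% |
| 1.10 | 0.1278 | 0.0769 | 38% |

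This table needs no model of persistence.

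**3. The denominator, by hand.** Assumptions: Ng and Ct split the rate equally (p = 0.1791/2 = 0.0896 per pathogen-visit), visits are independent, and a share c of unscreened positives is still positive at the next visit. The documents give no value for c. Baseline positivity per pathogen is (0.18 + 2×0.03)/2 = 0.12 in both arms.

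Counted events per pathogen over four visits, numerator-only rule:

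- Screened: 0.0896×0.88 + 3×0.0896×(1−0.0896) = 0.3234.
- Unscreened, 25% higher acquisition (0.1119), c = 0: 0.1119×0.88 + 3×0.1119×(1−0.1119) = 0.3967. Ratio 0.3967/0.3234 = 1.227, against a true 1.25.
- With c = 10%, the prior-positive shares at months 6, 9 and 12 are 0.112, 0.122 and 0.123. Events 0.3944, ratio 1.220.
- With c = 20%, they are 0.112, 0.132 and 0.135. Events 0.3919, ratio 1.212.

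The shortfall from 1.25 is 1.9%, 2.4% and 3.1%. At equal acquisition the same steps give 1.000, 0.995 and 0.990. With the denominator restricted to the same intervals, this simple model returns 1.25 and 1.00 exactly.

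**4. The same check with fewer simplifications.** A weekly-step simulation used the 11.1 risk classes, four assumed duration shapes on 1-6 months, an assumed 14% symptomatic and treated within a week, and perfect detection.

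| True acquisition ratio | Numerator-only | Both restricted |
|---|---|---|
| 1.00 | 0.98-1.00 | 0.99-1.01 |
| 1.25 | 1.17-1.20 | 1.19-1.23 |

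A second simulation of this kind gave 1.17-1.21 against 1.20-1.24 at a true 1.25. Without individual variation in risk, the chance of claiming non-inferiority at a true 1.25 was 5-6% against 3-5%. The matched rule kept 83-88% of screened-arm diagnoses and had 71-78% power at equal acquisition.

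**5. Why no power-loss figure follows.** In the first simulation, the 1-6 month shapes gave measured primary ratios of 1.05-1.17 at equal acquisition. Durations fixed at 2.5 months, or uniform on 1-4 months, gave 0.97-1.02. The documents do not choose between these.

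**The case against.** The plan is more open than a quick reading suggests. 11.1 states its equal-arms assumption, and the endpoint it sizes is the number of diagnoses, so the assumption already covers everything net, carry-over included. Protocol 4.3.1 and SAP 5.2 name the bias, give its direction correctly and pre-specify an analysis for it. Any non-inferiority size computed at 1.00 is conditional in this way. All of that stands, so the request on 11.1 is for a link and a table, not a correction.

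The size of carry-over rests on inputs that the documents lack. Low-abundance infections and pooled specimens (Protocol 8.10) may mean missed detections, which shrink the arm difference. With assumed sensitivities of 85% and 70%, the 1-6 month ratios fell to about 1.06-1.13 and 1.05-1.09. The arrested-immunity argument in Protocol 1 and 3 could offset carry-over altogether. The 1-6 month range is given for asymptomatic Ng, and no Ct duration is stated. This also stands.

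On the sensitivity analysis, the lean is small and the analysis is supportive. The matched rule is not perfect either: it still falls a little below 1.25 in the fuller simulations, and it conditions on a test made after randomisation. True, but it removes most of an avoidable lean at almost no cost.

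**Conclusion.** Two cheap improvements, minor to moderate in weight. First, the numerator-only rule pulls the rate ratio towards non-inferiority by about 2-3% at a true 25% excess and by 0-1% at equal acquisition in the hand calculation. The direction follows from the rule itself; the size depends on assumed durations. Second, the 80% at 912 is correct under its stated assumption, but equal acquisition satisfies that assumption only if carry-over is negligible or offset.

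Three stronger readings are not supported:

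- **The trial is underpowered, by a stated amount.** The duration distribution, test sensitivity and symptomatic fraction are not in the documents, and some plausible durations leave power close to the stated figure. No single loss should be asserted.
- **Footnote b is contradicted by the Background.** A range of one to six months includes durations shorter than the visit interval. It does not refute the footnote, but the two are not reconciled.
- **Carry-over could produce a false non-inferiority claim in the primary analysis.** It raises the unscreened count, so it works against such a claim, as the protocol says.

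**What to change.** **SAP 7 (and 5.2).** Define the sensitivity analysis per pathogen. Limit both the numerator and the offset to intervals whose prior scheduled test for that pathogen, with the baseline test serving for month 3, was negative. Apply the same rule in both arms and sum the pathogen-intervals over Ng and Ct. Assign between-visit diagnoses to the interval in which they fall. State how a missing prior test, or a visit recoded as not done under SAP 3, is handled; the simplest choice is that it does not qualify, in numerator and denominator alike. Do not also admit intervals whose prior infection was treated. That keeps higher-risk visits mainly in the screened arm; with strong individual variation in risk (gamma, variance 1) it gave 0.93-0.95 at equal acquisition. Name this analysis in advance as the aid to interpreting a failed primary result, without replacing the primary conclusion.

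**Protocol 11.1 and 4.3.1.** Add one sentence saying that the equal-arms assumption is net of carry-over, and the table of power by measured ratio. Give a number or a source for footnote b, and reconcile it and the Figure 5 text with the duration in Protocol 1.

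**Cost.** About 12-17% fewer screened-arm diagnoses in the sensitivity analysis, plus any out-of-window results treated as non-qualifying. No extra participants, visits or tests, and the primary endpoint is unchanged.
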